#### **4. Demographics and Other Baseline Characteristics**

The analysis and summary of all demographic and other baseline characteristics will be performed using the mITT population unless otherwise specified.

##### **4.1 Demographics**

Demographic data will be collected at the screening visit, including age, gender, race, weight, height, and body mass index (BMI). Age, weight, height and BMI will be analyzed with descriptive statistics (sample size, mean, SD, median, Min, and Max). Age group (18-35 years versus 36-50 years), gender, and race (Asian versus non-Asian) will be analyzed with frequency (counts and percentages).

Similar analyses will be done for the Safety population.

##### **4.2 Disease Characteristics**

For the mITT population, the distribution of the baseline MMPS will be summarized.

The distribution of the baseline lower facial width, mandibular facial angle, CT masseter muscle volume (total and defined region), investigator and subject LFSC will be summarized by treatment regimen for the mITT population.

##### **4.3 Prior and Concomitant Medications**

Prior medications include all medications taken prior to day 1 (randomization/treatment visit), whether or not the medication is continuing beyond day 1. Concomitant medications encompass all medicinal products that the subject was taking prior to the day 1 visit that are ongoing at the visit, in addition to all medications that have a start date on or after the day 1 visit date.

Prior and concomitant medication will be tabulated separately. The frequency (number and percentages) of subjects who have taken each medication will be tabulated for each treatment

regimen by MedDRA primary SOC, MedDRA HLT, and WHO DDE base preferred term. MedDRA SOC, HLT within each SOC, and WHO DDE base preferred term within each HLT will appear alphabetically.

If start or stop dates for medications are only partially reported but can be classified as prior to day 1, then the medications will be included in the summary of prior medications. If start or stop dates for medications are only partially reported and cannot be definitively classified as having stopped prior to day 1, then the medications will be included in the summary of concomitant medications.

#### **4.4 Concurrent Procedures**

All procedures undergone on or after study day 1 visit through the exit visit will be considered concurrent procedures. The frequency (number and percentage) of subjects who have undergone each procedure will be tabulated for treatment regimen by MedDRA HLT and preferred term. MedDRA HLT will appear alphabetically, and preferred term within each HLT will be sorted by descending incidence.

#### **4.5 Medical History**

Medical history includes all medical conditions that the subject has had in the past or currently has prior to injection on the day 1 visit. The frequency (numbers and percentage) of subjects reporting each medical history will be tabulated for the mITT population by MedDRA primary SOC in descending order.

#### **4.6 Dental History and Habits**

Dental history will be coded using the MedDRA dictionary. Dental history data will be summarized by preferred term using frequency distributions.

Descriptive statistics (sample size, count, percentage) will be presented for each dental habit.

Dental history and habits will be presented in the listing.

#### **4.7 Pretreatment Adverse Events**

Pretreatment adverse events (PTAEs) are defined as any adverse events with onset date prior to the first dosing of study medication. Pretreatment adverse events are discussed in Section [6.2](#).

## **5. Efficacy Analyses**

Pairwise comparisons will be done between each BOTOX group and the placebo group. A pairwise comparison will also be done between a BOTOX group and the next higher dose BOTOX group.

All subjects who received placebo will be pooled together as placebo group for analyses.

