# 3 Study Design

This is a multicenter, randomized, placebo-controlled, up to 2-treatment, dose-escalation study to assess a range of doses of BOTOX for the treatment of MMH. Up to 16 scheduled

visits are planned: screening (day -56 to day -1), day 1 (randomization/treatment), day 14 (telephone followup), monthly (days 30, 60, 90, 120, 150, 180 [possible retreatment]), and day 194 (telephone followup, only for subjects retreated at day 180), monthly (days 210, 240, 270, 300, and 330), and study exit (day 360).

After completion of all baseline study procedures and re-verification that the subjects meet all inclusion and exclusion criteria, subjects will be randomized and enrolled in cohorts of approximately 50 subjects each. Within each cohort, subjects will be randomized 4:1 to BOTOX (N = approximately 40) or placebo (N = approximately 10). Stratification will be by baseline (day 1) MMPS grade. Approximately 70% of the enrolled population in each cohort will be Asian, and subjects of Asian race will be further grouped by self-identified ethnicity (Chinese, Japanese, Korean, or other). Each cohort will be enrolled over approximately a 2-week period. When at least 50 subjects have been enrolled, randomization will be halted to allow observation of the cohort through the day 90 visit. The next cohort will be enrolled following a planned independent Data Review Committee (DRC) meeting (see Section 3.1) and Allergan's written notification to proceed.

On day 1, subjects will receive a single treatment of either BOTOX or placebo administered bilaterally to the masseter muscles as 3 injections/masseter in the area of maximal muscle bulge. The initial BOTOX total dose will be 24 U (12 U/masseter) and the maximum total dose will be 96 U (48 U/masseter). Table 2 shows the planned dose-escalation scheme.

Table 2 Dose Escalation by Cohort

Cohort	Total Dose	Target Sample Size	Target Total Subjects/Cohort
1	24 U	40	50
1	placebo	10	
2.	48 U	40	50
2	placebo	10	
2	72 U	40	50
3	placebo	10	
4	96 U	40	50
4	placebo	10	50

Based on the DRC assessment and provisions for retreatment, subjects who meet the retreatment criteria (see Section 5.10) at the day 180 visit may receive a second study treatment. The second treatment is only allowed at the day 180 visit, and the same dose as day 1 will be administered.

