#### 5.5 Method for Assignment to Treatment Groups/Randomization

At the screening visit, after the subject signs informed consent, the site will call the IVRS or log on to the IWRS to obtain a subject number and coded initials that will serve as the subject identification number on all study documents.

The IVRS/IWRS will be used to manage the randomization and assignment of subjects into 1 of the 2 treatment groups for each cohort based on a central randomization schedule prepared by Allergan Biostatistics prior to day 1. The randomization will occur after all baseline procedures have been completed and the investigator has re-verified that the subject has met all inclusion and exclusion criteria. Randomization will be stratified by the subject's baseline (day 1) MMPS grade (4 or 5), as assessed by the investigator.

Study treatment will be labeled with kit numbers. The IVRS/IWRS will provide the site with the specific kit number for each randomized subject at the time of randomization (day 1). The IVRS/IWRS will also issue the specific kit number for each subject who qualifies for retreatment on day 180. Sites will dispense study treatment according to the IVRS/IWRS instructions. Sites will receive the IVRS/IWRS confirmation notifications for each transaction that will be maintained with the study source documents.

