### **2.3.2 Baseline, Changes from Baseline and Direction of Differences**

The latest measurement taken on or before day 1 prior to the first injection will be the baseline measurement. In addition, within each treatment cycle, “cycle baseline” is defined as the most recent evaluation prior to the current cycle’s treatment. Changes from baseline will be based on the day 1 baseline (rather than cycle baseline) unless otherwise stated.

Change from baseline will be calculated as followup minus baseline. The interpretation of a positive or negative change from baseline is specific to the outcome measure and will be discussed as needed. Treatment differences will be reported as BOTOX minus placebo and as BOTOX (higher total dose) minus BOTOX (lower total dose).

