### **5.2 Primary Efficacy Analyses**

Descriptive statistics for change from baseline in lower facial volume for each study visit (sample size, mean, standard deviation, median, minimum, and maximum) will be provided by treatment regimen for all scheduled visits.

The primary efficacy analysis will be based on the mITT population. Day 90 is the primary timepoint.

The following set of hypotheses will be used to compare the BOTOX groups with placebo:

- Null hypothesis: BOTOX and placebo are equally effective in changing lower facial volume at day 90.
- Alternative hypothesis: BOTOX and placebo are not equally effective in changing lower facial volume at day 90.

The change from baseline in lower facial volume at each visit will be analyzed using an ANOVA model with treatment, and baseline MMPS grade as factors. In addition, 2-sided 95% confidence intervals for the treatment differences will be provided.

Analysis will also be performed based on observed data (ie, strictly data that falls within the visit windows) for the mITT population.

Among-group comparisons for the placebo groups will be analyzed using an ANOVA model with treatment as factor to test whether they are combinable. If the difference among the placebo groups are significant, sensitivity analysis will also be done for the primary variable using an ANOVA model with treatment, cohort number (as numeric variable) and baseline MMPS grade as factors.

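### Adjacent-dose contrasts compare cohorts that were enrolled months apart and never randomised against each other; the main models have no cohort term, and the only safeguard is conditional, linear and limited to the primary variable

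*SAP*

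**What the plan says.** **Design.** Protocol 5.5 describes "assignment of subjects into 1 of the 2 treatment groups for each cohort". Protocol 3 sets the ratio within a cohort at 4:1, about 40 BOTOX to 10 placebo, and Table 2 gives one dose per cohort (24, 48, 72, 96 U).

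**Timing (Protocol 3).** "Each cohort will be enrolled over approximately a 2-week period". Then: "When at least 50 subjects have been enrolled, randomization will be halted to allow observation of the cohort through the day 90 visit". And: "The next cohort will be enrolled following a planned independent Data Review Committee (DRC) meeting". The sponsor's written notification is also required.

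**Comparisons.** SAP 5 states: "A pairwise comparison will also be done between a BOTOX group and the next higher dose BOTOX group". SAP 2.3.1, 5.1 and 5.3 and Protocol 7.2 plan the same comparison. SAP 2.3.2 reports it as higher dose minus lower dose. SAP 2.3.7 sets 0.05, 2-sided, as the default for all tests.

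**Models.** Volume change is analysed "using an ANOVA model with treatment, and baseline MMPS grade as factors" (SAP 5.2). MMPS response uses a CMH test stratified by baseline MMPS grade (SAP 5.3). Neither has a cohort term.

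**Safeguard.** SAP 5.2 compares the placebo groups with each other. If they differ significantly, it adds a sensitivity ANOVA of the primary variable with treatment, cohort number as a numeric variable, and baseline MMPS grade. The adjacent-dose contrasts carry no caveat.

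**The concern.** A contrast such as 48 U minus 24 U is a comparison between two cohorts. The 4:1 randomisation protects the comparison of a dose with its own cohort's placebo; it does not protect one dose against another. If outcomes shift between cohorts for reasons other than dose (calendar time, case mix within an MMPS grade, imaging or grading practice), the main analysis cannot tell that shift from a dose effect. A shift in one direction creates an apparent dose difference, and a shift in the other hides a real one.

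There is also a route specific to the MMPS. Injection volume is fixed by cohort (Protocol 5.6, Table 3), and the investigator both injects and grades. The investigator stays blind to BOTOX versus placebo but may infer which dose level is under test.

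The study objective is a range of doses, and Protocol 1 says the study should help design later ones. Adjacent-dose p-values are what a reader would use to decide whether one dose separates from the next.

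**Working it through.** **Inputs.** 40 BOTOX and 10 placebo per cohort (Protocol 7.5); 2-sided 0.05 (SAP 2.3.7), used also for the placebo combinability test. Drift sizes are assumptions in outcome SD units, because the documents give none. Baseline MMPS is ignored except for its degree of freedom.

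**1. The plan's own figure.** Protocol 7.5 gives 93% power for 40 v 10, effect size 1, 1-sided 0.10. The noncentral t with 48 df gives 93.6%, so the figure reproduces. No power is stated for the adjacent-dose tests.

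**2. Planned contrast under drift.** The standard error (SE) is √(1/40 + 1/40) = 0.224 SD. With no cohort term, the bias equals the drift *d*. The rejection probability with no true dose difference is that of a noncentral t with noncentrality *d*/0.224. The two-group test (78 df) gives 7.3%, 19.7% and 59.8% at *d* = 0.1, 0.25 and 0.5. The full-model error (194 df) gives 7.3%, 19.9% and 60.5%.

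**3. Chance that the safeguard runs.** The test among four placebo groups of 10 is an F with 3 and 36 df. Its noncentrality is 10·Σ(cohort mean − overall mean)².
- Linear drift of *d* per cohort: 10·5*d*² = 50*d*², or 3.125 at 0.25 and 12.5 at 0.5.
- Single step *d* between cohorts 2 and 3: 10·1·*d*² = 10*d*², or 0.625 at 0.25 and 2.5 at 0.5.

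| Assumed drift (SD) | False significance, planned test | Safeguard runs: single step | Safeguard runs: linear drift |
|---|---|---|---|
| 0 | 5% | 5% | 5% |
| 0.1 | 7% | 5.5% | 8% |
| 0.25 | 20% | 8.5% | 26% |
| 0.5 | 60% | 21% | 81% |

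In 20,000 simulated trials with a single step, 48 v 72 U was falsely significant with no sensitivity analysis triggered in 18% of trials (0.25 SD) and 48% (0.5 SD).

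**4. What the safeguard removes when it runs.** Each dose sits in one cohort, so the cohort slope is estimated from placebo alone. Linear drift is removed completely. For a single step between cohorts 2 and 3, the fitted slope is (0.5 + 1.5)/5 = 0.4 of the step. The 48 v 72 U contrast therefore keeps 1 − 0.4 = 60% of the bias, and the other two contrasts each gain −40%. For a 0.5 SD step that is 0.30 SD left and −0.20 SD added to each of the others.

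**5. Precision of the alternatives.** The slope variance is 1/(10·5) = 1/50.

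| Contrast | SE (SD) | 95% half-width (about 1.97 × SE) | Power for a true 0.5 SD dose difference |
|---|---|---|---|
| Planned, no cohort term | √(2/40) = 0.224 | 0.44 | 61% |
| Linear cohort term | √(2/40 + 1/50) = 0.265 | 0.52 | 47% |
| Cohort as a factor (own-cohort placebo correction) | √(2(1/40 + 1/10)) = 0.500 | 0.99 | 17% |

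**The case against.** The best defence is that the SAP already foresees cohort differences. A reader of SAP 5 alone might infer that the placebo arms are never used against drift. SAP 5.2 shows otherwise: its cohort-number model applies a placebo-based correction to these contrasts at little cost in precision. The objection stands to that extent. The criticism is that the safeguard is too weak, as steps 3 and 4 show.

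Other stronger readings also go beyond the documents:
- *Any drift is confounded.* Too wide. A shift in the mix of grades 4 and 5 is handled by the MMPS term. The outcome is change from the subject's own baseline, using registered images (Attachment 12.1.2). Training and a consistent evaluator (Protocol 8.4) limit drift, though they do not exclude it.
- *Knowledge of the dose level biases the primary endpoint.* Lower facial volume is computed from images with landmarks verified by an analysis technician. The argument bears on the MMPS.
- *Different sites were active in different cohorts.* The protocol gives only a total of about 4 to 12 sites.
- *The main hypotheses fail.* They concern BOTOX versus placebo (SAP 5.2) and are not the subject here. Neither document says that the doses were randomised against each other.

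It is also fair to say that sequential enrolment is inherent in dose escalation, and that 95% intervals are already planned. That explains the design, but not the absence of a caveat or of an unconditional adjusted contrast.

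**Conclusion.** The point holds. In the main analyses, cohort drift not captured by baseline MMPS is fully confounded with adjacent-dose differences, and the existing safeguard would often not run or would correct the wrong pattern. MMPS response has no such safeguard in SAP 5.2 or 5.3.

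The size depends on the drift, which is unknown. At 0.1 SD the inflation is slight (7% against 5%); at 0.25 to 0.5 SD it is serious (20% to 60%). Nothing in the documents shows that drift of that order occurred. The calculations assume normal outcomes, target group sizes, and drift common to BOTOX and placebo subjects. Drift that acts only on treated subjects, such as a change in injection technique, could not be corrected from placebo by any model.

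This is a should-fix matter: it limits what can be concluded about dose separation.

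**What to change.** 1. In SAP 2.3.1, 5, 5.1, 5.2 and 5.3, state that dose-versus-next-dose contrasts are non-randomised and supportive. Report them as an estimate with a 95% interval and no claim of significance.
2. For day 90 volume change, whatever the placebo combinability test shows, report two adjusted contrasts beside each unadjusted one: the existing linear-cohort model (SE about 0.26 SD), and the model with cohort as a factor (SE about 0.50 SD). The second equals (higher dose minus its own cohort's placebo) minus (lower dose minus its own cohort's placebo).
3. For MMPS response, tabulate BOTOX and placebo responder rates by cohort, with the placebo-corrected difference shown as descriptive only.

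This takes SAP wording and a few extra contrasts from data already planned, with no change to conduct. The downside is imprecision: with about 10 placebo subjects per cohort, the fully corrected contrast has only 17% power for a 0.5 SD dose difference, and the MMPS version will be rough. Statements about dose separation become more modest.

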### **5.1 Collection and Derivation of Primary Efficacy Assessments**

The primary efficacy variable, change from baseline in lower facial volume (cm^3), is calculated from VECTRA M3 digital photography system 3D image models [REDACTED]

Visit windows for all time points are specified in Section 2.2. The primary time point is day 90 of the first treatment cycle.

Between group comparisons will only be performed for each BOTOX group against the placebo group, and for each BOTOX group against the next higher dose BOTOX group.

For analysis of the mITT population, the last observation carried forward (LOCF) method will be used to impute missing values.

### **5.2 Primary Efficacy Analyses**

Descriptive statistics for change from baseline in lower facial volume for each study visit (sample size, mean, standard deviation, median, minimum, and maximum) will be provided by treatment regimen for all scheduled visits.

The primary efficacy analysis will be based on the mITT population. Day 90 is the primary timepoint.

The following set of hypotheses will be used to compare the BOTOX groups with placebo:

- Null hypothesis: BOTOX and placebo are equally effective in changing lower facial volume at day 90.
- Alternative hypothesis: BOTOX and placebo are not equally effective in changing lower facial volume at day 90.

The change from baseline in lower facial volume at each visit will be analyzed using an ANOVA model with treatment, and baseline MMPS grade as factors. In addition, 2-sided 95% confidence intervals for the treatment differences will be provided.

Analysis will also be performed based on observed data (ie, strictly data that falls within the visit windows) for the mITT population.

Among-group comparisons for the placebo groups will be analyzed using an ANOVA model with treatment as factor to test whether they are combinable. If the difference among the placebo groups are significant, sensitivity analysis will also be done for the primary variable using an ANOVA model with treatment, cohort number (as numeric variable) and baseline MMPS grade as factors.

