# 7.2 Collection and Derivation of Primary and Secondary Efficacy Assessments

Efficacy results for all study visits will be summarized based on time since injection. Visit windows for all timepoints will be described in the statistical analysis plan.

Pairwise comparisons will be done between each BOTOX group and the placebo group. A pairwise comparison will also be done between a BOTOX group and the next higher dose BOTOX group. For interim analyses, subjects in the placebo group(s) from previous cohort(s) will be pooled with the placebo group from the current cohort for analysis if the results for the placebo groups are combinable. For final analysis, all subjects who received placebo will be pooled together as a total placebo group if the results for the placebo groups are combinable. Details will be specified in the Analysis Plan.

The primary efficacy variable will be the lower facial volume at day 90. The change from baseline in lower facial volume will be analyzed by analysis of variance (ANOVA) with treatment and baseline (day 1) MMPS grade as factors to assess the response between groups.

For analysis of the mITT population, the last observation carried forward (LOCF) method will be used to impute missing values. For analysis of the PP population, observed data without imputation will be used.

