## 7.5 Sample Size Calculation

The sample size used in this study is determined empirically.

For each cohort, 40 subjects will be randomized to BOTOX, and 10 subjects will be randomized to placebo. Assuming the VECTRA lower facial volume is a normal distribution and the effect size is 1, a 1-sided test with 0.10 significance level will have 93% power to detect a statistically significant change in the BOTOX group compared with the placebo group. The commercial software nQuery version 6.01 procedure MTT0U-1 was used for the power calculation.

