### 1.1 Primary Study Objectives and Design

The objectives of this study are to evaluate the safety and efficacy of a range of doses of BOTOX for the treatment of subjects with bilateral masseter muscle hypertrophy (MMH).

This study is a multicenter, randomized, double-blind, placebo-controlled, up to 2-treatment, dose escalation study. BOTOX or placebo will be administered intramuscularly to the bilateral masseter muscles (6 total injections, 3 injections/masseter). The initial BOTOX total dose will be 24 U (12 U/masseter) and the maximum BOTOX total dose will be 96 U (48 U/masseter). Stratification will be by baseline (day 1) Masseter Muscle Prominence Scale (MMPS) grade at baseline (day 1). The planned dose escalation is as follows:

Cohort	Total Dose	Sample Size	Total Subjects/Cohort
1	24 U	N=40	50
	placebo	N=10	
2	48 U	N=40	50
	placebo	N=10	
3	72 U	N=40	50
	placebo	N=10	
4	96 U	N=40	50
	placebo	N=10	

The second treatment is only allowed at the day 180 visit. Subjects will receive the same treatment as they received at the day 1 visit.

Subjects who meet the following retreatment criteria at the day 180 visit will receive a second treatment:

- Allergan written notification allowing retreatment of the current cohort

- subject has marked (grade 4) or very marked (grade 5) bilateral masseter muscle hypertrophy, as assessed by the investigator using the MMPS
- females of childbearing potential must have a negative urine pregnancy test prior to treatment

The primary efficacy variable, change from baseline in lower facial volume ( $\text{cm}^3$ , note that  $1\text{cm}^3=1\text{mL}$ ), is calculated from VECTRA M3 digital photography system 3D image models

[REDACTED]

The primary safety analysis is the calculation of incidence of treatment emergent adverse events (TEAE) for the entire study period, as well as for each treatment cycle.

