### **2.3.1 Treatment Group and Treatment Cycles**

A treatment cycle is considered to start on the day of treatment with study medication and end on the day prior to the next study treatment or on the study exit day if there are no subsequent treatments.

Between group comparisons will only be performed for each BOTOX group against the placebo group, and for each BOTOX group against the next higher dose BOTOX group.

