### **2.3.5 Handling Drop-out or Missing Data**

For efficacy analyses of mITT population of the change from baseline in lower facial volume using VECTRA 3D images, MMPS, lower facial width, mandibular facial angle, CT masseter muscle volume, LFSC, and LFSQ, last observation carried forward (LOCF) will be used to impute missing values for each scheduled visit. Only missing data for visits up to day 180 of each treatment cycle will be imputed. Missing data for visits after day 180 of each cycle will not be imputed. If a subject exited the study before day 180 of a treatment cycle, visits after the study exit will not be imputed.

Missing baseline values for lower facial width, mandibular facial angle, CT masseter muscle volume, LFSC, and LFSQ will be imputed using the average of subjects with non-missing values. Missing values for change from baseline in lower facial volume using VECTRA 3D images at day 30 will be imputed using the average of subjects with non-missing values.

For angle measurements, the average degree from both sides of the face will be determined first; if the degree of angle is missing for 1 side of the face, then the angle for the subject will be based on the angle of the other side of the face. If a subject's average is a half-degree value, it will be rounded up to an integer (eg, 30.5 degree will be rounded up to 31 degrees).

For rating an individual's MMPS score, the average of the scores from both sides of the face will be determined first; if a score is missing for 1 side of the face, then the score for the subject will be based on the score of the other side of the face. If a subject's average is a half-grade value, it will be rounded up to an integer to remain consistent with the original scale (eg, 1.50 will be rounded up to 2).

When implemented, imputation of missing values will be performed only for subjects who receive a treatment in the pertinent treatment cycle. For example, only subjects receiving the second treatment will have values imputed in treatment cycle 2; subjects who discontinued from the study during the first treatment will not have any data imputed in treatment cycle 2.

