### **5.3 Secondary Efficacy Analyses**

The secondary efficacy variable is the investigator’s assessment of MMH using the MMPS (1 = minimal, 2 = mild, 3 = moderate, 4 = marked, 5 = very marked).

The proportion of responders will be analyzed with a responder defined as subjects who achieve an MMPS grade of  $\leq 3$ . The proportion of responders will be analyzed using Cochran-Mantel-Haenszel (CMH) tests stratified by baseline MMPS grade. In addition, 2-sided 95% confidence intervals for the treatment differences in response rates will be provided. Between group comparisons will only be performed for each BOTOX group against the placebo group, and for each BOTOX group against the next higher dose BOTOX group.

[REDACTED]

[REDACTED]

[REDACTED]

[REDACTED]

[Redacted text block]

[Redacted text block]

[Redacted text block]

[Redacted text block]

[Redacted text block]

[Redacted text block]

[Redacted text block]

[Redacted text block]

[Redacted text block]

[Redacted text block]

[Redacted text block]

[Redacted text block]

[Redacted text block]

[Redacted text block]

[Redacted text block]

[Redacted text block]

[Redacted text block]

[Redacted text block]

[Redacted text block]

[Redacted text block]

[REDACTED]

[REDACTED]

[REDACTED]

[REDACTED]

[REDACTED]

[REDACTED]

[REDACTED]

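### Where retreatment is permitted, between-arm efficacy tests after day 180 compare groups selected on day 180 MMPS grade, not the randomised groups

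*SAP*

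**What the plan says.** Protocol 7.2 sets the time axis: "Efficacy results for all study visits will be summarized based on time since injection". SAP Section 11 lists no deviation from Protocol Section 7, so that axis carries over. SAP 2.3.1 has a treatment cycle start on the treatment day and "end on the day prior to the next study treatment or on the study exit day if there are no subsequent treatments".

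SAP 2.3.5 recognises visits late in a cycle: "Missing data for visits after day 180 of each cycle will not be imputed". It also restricts imputation in cycle 2 to subjects who had the second injection. SAP 2.3.2 measures change from the day 1 baseline by default, in cycle 2 as well.

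SAP 5.2 plans the volume test without a limit on visits: "The change from baseline in lower facial volume at each visit will be analyzed using an ANOVA model", with 95% confidence intervals for treatment differences. For MMPS response, defined as grade 3 or less, SAP 5.3 says: "The proportion of responders will be analyzed using Cochran-Mantel-Haenszel (CMH) tests stratified by baseline MMPS grade". It names no visit.

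Retreatment is possible only at day 180. One of its criteria (SAP 1.1, Protocol 5.10) is that the "subject has marked (grade 4) or very marked (grade 5) bilateral masseter muscle hypertrophy, as assessed by the investigator using the MMPS". The others are written clearance by the sponsor for that cohort and, for women of childbearing potential, a negative pregnancy test.

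**The concern.** Read together, these rules divide subjects at day 180 by an outcome. A retreated subject's day 210 to 360 visits become days 30 to 180 of cycle 2. Only subjects who were not retreated supply cycle 1 data after day 180. Retreatment depends on the same scale, at the same visit, that defines response.

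A between-arm ANOVA or CMH test on either part then conditions on a post-randomisation outcome that treatment itself affects. The few placebo subjects at grade 3 or less at day 180 are compared with a larger and less extreme share of BOTOX subjects. In cycle 2, nearly all placebo subjects would be compared with the BOTOX subjects whose effect had worn off or never appeared.

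The protocol background says the trial should help design later studies. A team reading these tables as duration or repeat-dose results, by dose, could be misled.

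**Working it through.** **Plan's own figure.** Protocol 7.5 gives: "Assuming the VECTRA lower facial volume is a normal distribution and the effect size is 1", and "a 1-sided test with 0.10 significance level will have 93% power to detect a statistically significant change", with 40 BOTOX and 10 placebo subjects. The noncentrality is 1/√(1/40 + 1/10) = 2.83 with 48 df, which gives 93.6% power. The figure is reproduced. The calculation names no visit after day 180, so it supplies only a planning effect size of 1.

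**Overlap of the two rules.** SAP 2.3.5 averages the left and right grades and rounds half grades up. Of the 25 left/right pairs:
- 15 score 3 or less (responder);
- 4 have both sides at 4 or 5 (MMPS-eligible for retreatment);
- none is both;
- 6 are neither: (3,4), (3,5), (2,5) and their mirror images. Each scores 4 but is not bilaterally grade 4 or more.

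So cycle 2 holds only day 180 non-responders. Late cycle 1 holds day 180 responders, plus subjects with those asymmetric grades and others not retreated (for example, because of pregnancy).

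**Group sizes.** The documents give no day 180 response rates, so these are assumptions. Take 40 per dose and 4 × 10 = 40 pooled placebo, every cohort cleared, and no asymmetric grades. Power is for effect size 1, 2-sided 0.05.

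| Day 180 responders, BOTOX / placebo | Late cycle 1 n | Power |
|---|---|---|
| all subjects, no selection | 40 vs 40 | 99% |
| 20% / 5% | 8 vs 2 | 20% |
| 50% / 10% | 20 vs 4 | 42% |
| 70% / 20% | 28 vs 8 | 68% |

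**Bias in volume at day 180.** Let volume reduction and latent MMPS improvement be bivariate normal in each arm, with unit variance and correlation ρ. Let d be the true volume difference and p the arm's responder share. Put z = Φ⁻¹(p) and λ(p) = φ(z)/p. Among day 180 responders,

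expected difference = d + ρ[λ(p_BOTOX) − λ(p_placebo)].

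Values of λ: 2.063 (5%), 1.755 (10%), 1.400 (20%), 0.966 (40%), 0.644 (60%), 0.497 (70%). For d = 0.5:
- placebo/BOTOX 10/60%, ρ = 0.5: 0.5 + 0.5(0.644 − 1.755) = −0.06 SD
- 10/60%, ρ = 0.7: 0.5 + 0.7(0.644 − 1.755) = −0.28 SD (lowest)
- 20/70%, ρ = 0.3: 0.5 + 0.3(0.497 − 1.400) = 0.23 SD (highest)

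Over shares of 5/40%, 10/60% and 20/70% and ρ of 0.3, 0.5 and 0.7, d = 0.5 appears as −0.28 to 0.23 SD. Adding 0.5 throughout, d = 1.0 appears as 0.22 to 0.73 SD. These figures describe the day 180 subsets. They model neither a later visit nor the second injection.

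**Response at a later visit, late cycle 1 only.** A separate simulation linked latent status at day 180 and day 270. Assume 50% vs 20% responding at day 180 and 35% vs 20% at day 270 if nobody were retreated, a true difference of 15 points. Among day 180 responders the difference becomes +7, +1 or −9 points for within-subject correlations of 0.5, 0.7 or 0.9. Over four assumed scenarios, true differences of +10 to +30 points became −9 to +18.

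**The case against.** The strongest reply is that the efficacy split is inferred. SAP 5.2 says only that volume is tested at each visit. The one explicit split by second injection is for CT safety (SAP 6.5). SAP 2.2, the visit windows, is not in the text available, and much efficacy text after SAP 5.3 is redacted. This stands as a limit: it cannot be said that the plan has no duration analysis. The readable rules still point one way. If late visits were instead pooled by study day, the randomised groups would be kept, but retreated and non-retreated subjects would be mixed, and single-treatment duration would still not be isolated.

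A reader might also infer four stronger things that the documents do not support.
- *Late cycle 1 holds exactly the day 180 responders, so every arm starts near 100%.* Asymmetric grades break this. With 4 placebo responders, two such subjects make it 4/6 = 67%. Cohorts not cleared for retreatment have no selection at all, and placebo is pooled across cohorts.
- *The trial cannot show duration.* Monthly visits through day 180 precede retreatment and keep the randomised groups, so persistence to about six months can be estimated.
- *The volume effect reverses.* That depends on inputs. The assumed shares imply latent MMPS effects of about 1.4 to 1.5 SD, set beside a volume effect of 0.5 SD. At the planning effect of 1 the same model gives attenuation only. Cycle 2 after re-dosing is not modelled.
- *Responder tests are certainly run at late visits.* SAP 5.3 gives no timepoint for the CMH test.

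**Conclusion.** The point holds in limited form. In cohorts where retreatment is permitted, the readable rules make cycle 1 after day 180 and all of cycle 2 subsets selected on day 180 MMPS grade. Between-arm volume tests there are not randomised comparisons, nor are responder tests if CMH is run at those visits. Neither can support a claim about duration beyond day 180 or about a randomised repeat-dose effect.

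The direction of the problem rests on the documents; its size does not. For MMPS the selection acts on the endpoint itself. For volume it acts through a correlation that the documents do not give. The numerical ranges above are illustrations under assumed response rates and correlations.

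The day 90 primary analysis is untouched. What is affected is secondary late-visit output in a phase 2 study, which is still worth correcting because the change is small.

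**What to change.** In SAP 5.2 and 5.3:

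1. Limit inferential between-group comparisons to cycle 1 visits through the day 180 assessment made before any retreatment.
2. Present cycle 1 after day 180, and cycle 2, as descriptive summaries without p-values, labelled as subsets selected on day 180 MMPS grade.
3. If single-treatment duration beyond day 180 is to be compared, analyse all mITT subjects by day 1 group. Count as a responder at a later visit only a subject who was a responder at day 180 and is one at that visit. Day 180 non-responders are then treated alike whether or not their cohort was cleared for retreatment. A rule that merely scored retreated subjects as failures would not do this, and because cohort is tied to dose, the endpoint could then differ by dose. State also how a day 180 responder with a missing later visit is counted, since SAP 2.3.5 leaves those visits unimputed.

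If SAP 2.2 or the redacted text already contains such rules, a cross-reference from 5.2 and 5.3 is enough. The cost is SAP wording and, if item 3 is used, one table from data already collected. The late-visit p-values are lost. The retreatment rule itself is not changed.
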